2.3.2 Known Potential Benefits

Participants may receive direct benefit from being provided with the results of an exercise stress test and exercise prescription. Results are shared with each participant's cardiologist and entered under "research" in their medical record. Participants could also gain benefit from increasing their levels of PA. Finally, the information learned from the study could benefit future adolescent and adult CHD survivors by possibly identifying a feasible, accessible, and acceptable intervention that can improve PA engagement in a population at risk for significant future cardiovascular morbidities.

3 OBJECTIVES

3.1 Study Objectives

A total of 125 CHD survivors (ages 15 - 25), and caregivers for adolescent participants, are anticipated to be enrolled in Phase 1 of the study, which establishes eligibility for Phase 2. For Phase 2, the randomized trial portion of the study, we plan to enroll a total of 70 adolescents and caregiver, and 30 emerging adults. The aims of the study are to:

1. *Aim 1: Assess feasibility of the intervention to participants based on subjective ratings.*
Hypothesis 1: Participants are hypothesized to rate the intervention as not burdensome, easy to access, and appealing. Additionally, recruitment and retention rates are predicted to be $\geq 75\%$.
2. *Aim 2: Evaluate preliminary efficacy of the intervention on time spent in MVPA and SB, as well as improvement in cardiorespiratory fitness as assessed by changes in VO_{2max} .*
Hypothesis 2: Participants in the intervention arm will (A) increase MVPA relative to those in the comparison arm at post-intervention, (B) decrease SB relative to those in the comparison arm, and (C) demonstrate an increase in VO_{2max} at post-intervention relative to those in the comparison arm.
3. *Aim 3 (Exploratory): Explore mechanisms of change in MVPA and SB, as specified by the Theory of Planned Behavior, including attitudes (i.e., knowledge about and belief in positive outcomes from PA), normative beliefs (i.e., participant-report of family/friend/physician beliefs about and support of PA) and perceived behavioral control (i.e., barriers and efficacy for PA).*

3.2 Study Outcome Measures

3.2.1 Primary Outcome Measure

Number of minutes spent in MVPA as measured by an accelerometer.

3.2.2 Secondary Outcome Measures

Number of minutes spent being sedentary as measured by an accelerometer.

Maximal oxygen utilization during PA as measured by VO_{2max} during an exercise stress test.

3.2.3 Other Outcome Measures

Health-related quality of life as measured by the Patient-Reported Outcomes Measurement Information System (PROMIS).⁴⁵⁻⁴⁷

Self-reported PA as measured by the International Physical Activity Questionnaire (IPAQ).^{48,49}

3.2.4 Purported Mechanisms

PA attitudes as measured by the Benefits of PA questionnaire⁵⁰.

PA subjective norms as measured by the PA Subjective Norms⁵¹ and the Social Support for PA⁵² surveys.

PA perceived control as measured by the Barriers to Exercise survey⁵³ and the Self-Efficacy for Exercise Scale.⁵⁴

3.2.5 Other Exploratory Predictors

Cardiac-related anxiety as measured by the Cardiac Anxiety Questionnaire.⁵⁵

Self-consciousness of body due to cardiac interventions scars as measured by the modified Body Image Disturbance Questionnaire.⁵⁶

Caregiver perceptions of adolescents' health as measured by the Child Vulnerability Scale.⁵⁷

Caregiver perceptions of family discord as measured by the Family Environment Scale.⁵⁸

Caregiver perceptions of adolescents' PA as measured by the PA Norms survey.⁵¹

Caregiver self-reported PA as measured by the IPAQ.⁴⁸

Caregiver health-related quality of life as measured by the PROMIS.⁴⁵⁻⁴⁷

4 STUDY DESIGN

This single-site study is a randomized clinical trial of a Fitbit and exercise prescription vs. a Fitbit, exercise prescription, AND videoconferencing sessions with a PA coach over the course of 8 sessions in 20 weeks.

For Phase 1, participants are asked to complete less than 30-45 minutes of questionnaires wear an accelerometer for 7 days, and undergo an exercise stress test. For adolescent participants, a caregiver is asked to complete 20-30 minutes of questionnaires. Once the exercise stress test is completed and the accelerometer is returned, participants are compensated \$100. Once caregivers complete the online questionnaires, they are compensated \$20. Parking and mileage reimbursement to/from the hospital is provided.

If a participant engages in less than 60 minutes of MVPA per day and has no contraindications on the exercise stress test, he/she is approached for participation in Phase 2. Once recruited, participants receive a Fitbit and an explanation of their exercise prescription based on the results of their exercise stress test as provided by an exercise physiologist. Next, study staff open an envelope (pre-prepared by the study statistician, [name]) to reveal the participant's study arm designation.

Participants are randomized to 1 of 2 arms: the comparison arm, which receives a Fitbit and the exercise prescription, or the intervention arm, which also receives a Fitbit and exercise prescription PLUS videoconferencing sessions (e.g., FaceTime, Google Hangouts or Skype) with a PA coach (8 sessions over the course of 20 weeks). Each session lasts approximately 30 minutes and is audiotaped. The intervention arm focuses on changing attitudes (e.g., identifying pleasurable physical activities), perceptions of social norms of PA (e.g., problem-solving ways to receive support from family and friends) and perceptions of control for engaging in PA (e.g., increasing self-efficacy through goal setting and reducing barriers), as outlined by the Theory of Planned Behavior, to increase time spent in MVPA and decrease SB. The Fitbit is used to facilitate goal setting and self-monitoring for participants in the intervention arm.

During the course of the study, participants in both arms are asked to participate in an interim assessment (between weeks 8-12), which includes 30-45 minutes of questionnaires and wearing an accelerometer for 7 days, for which they are compensated \$50. Between weeks 20 and 26, participants in both arms are asked to engage in a post-intervention assessment, consisting of 30-45 minutes of questionnaires, wearing an accelerometer for 7 days, and undergoing a final exercise stress test. Caregivers are asked to complete 20-30 minutes of surveys at the post-intervention

assessment. Adolescents are compensated \$100 and caregivers are compensated \$20. Parking and mileage to/from the hospital is compensated for their final exercise stress test. Upon completion of the post-intervention assessment, participants randomized to the intervention arm will be asked to participate in focus groups lasting approximately 1.5 hours, to discuss their study experiences. There will be 3-4 groups that meet via videoconferencing with 6-8 participants per group. Participants who attend the focus group will be compensated \$50. Six months after their week 22 participants will be asked to complete a 6-month follow-up assessment, which consists of completing less than one hour of questionnaires and wearing an accelerometer for 7 days, for which they will be compensated \$75.

Medical information also is collected from participants' online medical records to consider as covariates or moderators of the treatment effect, including sex and indicators of disease status (e.g., diagnosis, surgical history, functional class, number of medications, comorbidities, and the number of hospitalizations in the past year).

Physical activity coaches are graduate students pursuing advanced degrees in medicine, exercise physiology, or other health-related fields. They have undergone over 16 hours of training prior to working with the first participant and have completed all required human subjects training.

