5 STUDY ENROLLMENT AND WITHDRAWAL

The total target sample size for enrollment in Phase 1 is 125 participants and in Phase 2, 100 participants (50 participants per arm). A higher enrollment is expected for Phase 1 than Phase 2 to account for some participants being deemed ineligible to proceed with Phase 2.

Potential participants are identified through upcoming cardiology clinic rosters who meet the age (15-25 years of age) and diagnosis (moderate to complex CHD³) criteria. Study personnel check the patient's medical record to verify eligibility. If a patient appears to be eligible, study staff confirm with the attending cardiologist that no additional reason/s preclude the adolescent from participating, including limitations to engaging in MVPA. Next, the patient, or if an adolescent, the patient's caregiver(s) (or their legal guardian of record), is sent a letter from the attending cardiologist, notifying them about the study and that study personnel will be in contact. An "opt out" phone number is provided so that the caregiver(s) can call and leave a message if they do not wish to be contacted. Approximately 1 week later, if no message was received, caregiver(s) are called by study personnel. During the phone conversation, the objectives and primary components of the study are discussed. If a patient and/or caregiver are interested, verbal consent/assent (if <18 years of age) is obtained for completing online questionnaires and the exercise stress test at NCH is scheduled. During the stress test visit, written consent/assent for the stress test and accelerometer assessment is obtained. If a patient and/or a caregiver cannot be reached via phone, they are approached during their clinic appointment in person.

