5.6 Accountability Procedures for the Study Intervention

Individual and group supervision sessions are held for coaches to clarify study procedures, receive feedback on interactions with participants, and share ideas for ways to trouble-shoot around barriers to PA that participants broach during session. [name], who is familiar with the study but is not directly involved, as well as another study staff member, will listen to a random selection of 2 audiotaped sessions per participant and rated on their fidelity. Fidelity <90% triggers retraining of the interventionist as to the study materials.

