7.6 Study Hypotheses

Hypothesis 1: Participants are hypothesized to rate the intervention as not burdensome, easy to access, and appealing. Additionally, recruitment and retention rates are predicted to be $\geq 75\%$.

Hypothesis 2: Participants in the treatment arm will (A) increase MVPA relative to those in the comparison arm at post-intervention, (B) decrease SB relative to those in the comparison arm, and (C) demonstrate an increase in VO_{2max} at post-intervention relative to those in the comparison arm.

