7.7 Sample Size Considerations

A sample size of $n=50$ per group will provide 80% power to detect a large effect size⁵⁹ for the standardized mean difference, still allowing for possible detection of a medium effect size ($d=.6$) with 55% power. Effect sizes from relevant studies examining change in MVPA range from large ($d=.94$; CHD adolescents in a motivational interviewing-style exercise intervention)²⁸ to small ($d=.17$; older adults with cardiovascular risk factors).²² Thus, our primary goal is to estimate an initial effect size for our intervention in our population, with a secondary goal to detect large effect sizes that may exist for study outcomes. However, effect estimation with a relatively small sample size should be interpreted with caution, as it may under or overestimate the sample size.^{60,61}

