7.9 Analysis Plan

Aim 1: Evaluate the feasibility of the intervention.

The mean/median ratings by participants on multiple dimensions of the intervention will be computed. Recruitment rate will be calculated as a percentage of those recruited out of those approached. Percent adherence across sessions will be calculated for those in the intervention arm as the number of sessions attended out of 8. The retention rate will be identified by dividing the number of participants who do not complete the study by the number of participants enrolled.

Verbal responses collected during the focus groups will be transcribed and then coded so that the frequencies of suggestions can be calculated.

Aim 2: Examine preliminary efficacy of the intervention on time spent in MVPA.

First, independent sample t-tests (continuous variables) or chi-square tests (categorical variables) will compare study arms on all variables at baseline, *including biological considerations such as sex and disease status*, to determine if statistically significant differences are present. Only the pre-specified covariates of baseline minutes spent in MVPA and baseline VO_{2max} will be included in the primary analyses.⁶² However, if statistically significant differences are found at baseline, those variables will be examined as covariates in all statistical models of interest in an exploratory fashion.

Second, the following statistical model for repeated measures (RM), based on maximum likelihood estimation, will be employed,⁶³ $y_{it} = \beta_0 + \beta_1 Time_t + \beta_2 Time_t \times Trt_i + \varepsilon_{it}$, where implicitly it is assumed that there is no main effect of Trt_i , y_{it} is minutes in MVPA at time t , $Time_t$ is coded as 0 for baseline and 1 for post-intervention, and the primary effect of interest is β_2 , which is the difference between groups on participants' minutes in MVPA. In this RM model, baseline levels of minutes in MVPA is constrained to have equal means across groups by assuming there is no main effect of the intervention, Trt_i . This constraint yields a statistical test for β_2 analogous to the test of the treatment group main effect per ANCOVA without requiring list-wise deletion to account for missing data. A similar strategy will be taken for analyzing change in SB and VO_{2max} as secondary outcomes.

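### More than one coach delivers the intervention, in one arm only, and the Aim 2 model has no coach term, so the standard error of beta2 will be too small if coaches differ in their effect on MVPA

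*Combined protocol and SAP*

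**What the plan says.** **Who has a coach.** Sections 4 and 5.4 give the intervention arm eight videoconferencing sessions over 20 weeks. The comparison arm receives the Fitbit and the exercise prescription without sessions, and Section 5.7 adds that it is not contacted about the Fitbit again.

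**Who the coaches are.** Section 4: "Physical activity coaches are graduate students pursuing advanced degrees in medicine, exercise physiology, or other health-related fields". Section 5.6: "Individual and group supervision sessions are held for coaches". There is therefore more than one coach. No section says how many, how participants are allocated to them, or whether a participant keeps the same coach.

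**How delivery is standardised.** Sections 4 and 9 require more than 16 hours of training. Section 5.4.1 sets the content of each session. Sections 5.6 and 9 have two recorded sessions per participant rated for fidelity, and Section 5.6 requires retraining below 90%.

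**How efficacy is analysed.** In Section 7.9, Aim 2, "the following statistical model for repeated measures (RM), based on maximum likelihood estimation, will be employed". The terms are time, time by treatment and a residual, and beta2 is the effect of interest. The pre-specified covariates are baseline MVPA and baseline VO2max. Neither Section 7.9 nor Section 7.7 mentions a coach effect, a clustered standard error, an ICC or a design effect.

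**The concern.** This is a partially nested design: participants in one arm share therapists and those in the other arm have none. If some coaches are better than others at raising MVPA, participants with the same coach tend to do well or badly together. Fifty intervention participants then carry less information about the treatment effect than fifty independent ones. The repeated-measures structure is meant to deal with correlation within a participant over time; nothing in it deals with correlation between participants who share a coach.

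Section 7.7 makes estimation of an initial effect size the primary goal, and Section 2.2 says the pilot data will shape the next investigation. The uncertainty around beta2 is thus one of the trial's main products. A later trial of the same coached intervention would also need some idea of the coach-level variance for its sample size, and the present plan would not estimate it. If coach ID is not kept with the participant record, the analysis may not be possible afterwards.

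**Working it through.** **The plan's own figures.** The plan prints no coach-related number, so there is none to reproduce. Its power statement bears on this point only as a possible hidden allowance for clustering. Section 7.7 says the planned sample "per group will provide 80% power to detect a large effect size", with 55% power at d = 0.6. With 50 per arm, two-sided alpha 0.05 and d = 0.8 for large (alpha and that d are assumptions), the two-sample t-test gives 97.7% and 84.4%. The printed pair matches about 25 per arm (79.1% and 54.7%). That mismatch is a separate matter.

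**Inputs from the documents.** 50 participants per arm (Section 5); retention predicted to be at least 75% (Section 7.6); coaching in one arm only (Sections 4 and 5.4); no coach term (Section 7.9).

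**Assumed inputs.** Number of coaches k and coach ICC, neither of which is stated; equal caseloads; one coach per participant; coaches regarded as a sample from those who might deliver the programme.

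**Formulas.** With n analysed per arm:

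- Design effect in the intervention arm: DE = 1 + (n/k − 1) × ICC.
- The variance of beta2 is proportional to (DE + 1)/n, against 2/n under independence.
- True SE / planned SE = sqrt((DE + 1)/2).
- Actual size of a nominal two-sided 5% test = 2 × (1 − Φ(1.96/ratio)).

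**Numbers at n = 50.**

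- k = 10, ICC 0.01: DE = 1 + 4 × 0.01 = 1.04; ratio = sqrt(1.02) = 1.010; size 5.2%.
- k = 5, ICC 0.05: DE = 1 + 9 × 0.05 = 1.45; ratio = sqrt(1.225) = 1.107; size 7.7%.
- k = 3, ICC 0.05: DE = 1 + 15.67 × 0.05 = 1.783; ratio = sqrt(1.392) = 1.180; size 9.7%.

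The wider grid, as ratio (size):

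| Coaches | ICC 0.01 | ICC 0.02 | ICC 0.05 | ICC 0.10 |
|---|---|---|---|---|
| 3 | 1.04 (5.9%) | 1.08 (6.8%) | 1.18 (9.7%) | 1.34 (14.2%) |
| 5 | 1.02 (5.5%) | 1.04 (6.0%) | 1.11 (7.7%) | 1.20 (10.4%) |
| 10 | 1.01 (5.2%) | 1.02 (5.5%) | 1.05 (6.2%) | 1.10 (7.4%) |

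With ICC = 0 the ratio is 1 whatever the number of coaches. A ratio of 1.18 means that the true SE is 18% larger than the planned one or, equivalently, that the planned SE is 1 − 1/1.18 = 15% too small.

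**At 75% retention** (n = 37.5 per arm):

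- k = 5, ICC 0.05: DE = 1 + 6.5 × 0.05 = 1.325; ratio = sqrt(1.1625) = 1.08; size 6.9%.
- k = 3, ICC 0.05: DE = 1 + 11.5 × 0.05 = 1.575; ratio = sqrt(1.2875) = 1.13; size 8.4%.

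**Simulation check.** A baseline-adjusted independence model, with an assumed baseline-to-post correlation of 0.5 and ICC 0.05, rejected a true null in 11.8% of trials with 3 coaches, 7.9% with 5 and 6.4% with 10. The closed form is therefore a guide, and is not exact. An analysis of coach means with Satterthwaite degrees of freedom held 4.6% to 5.4% with 5 or 10 coaches but ran at 5.7% to 7.4% with 3.

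**The case against.** The strongest reply is that the problem may be negligible here. Coaches are trained, follow set session content, are supervised and are rated, all of which should lower the ICC. Enrolment is planned over three years with graduate-student coaches, so a large number of coaches, or a change of coach, fits the text as well as a small number does. With 15 coaches and ICC 0.05, DE = 1 + 2.33 × 0.05 = 1.117 and the ratio is sqrt(1.058) = 1.03, with size 5.7%. All of this stands as a limit on the size. It does not make the variance zero: fidelity ratings measure adherence to the session protocol, whereas the ICC concerns effects on MVPA.

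A second reply is that a random coach effect serves inference to other coaches, while Section 7.7 speaks of an effect size for this intervention in this population. This also stands in part. If the trial's own coaches are the only ones of interest, the wider interval is not needed. Planning a further trial, which is the stated purpose, points to the wider target, and the plan should say which it wants.

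A third reply is that the remedy is weakest where the problem is largest. With about three coaches the variance is barely estimable, and the corrected analysis remained slightly liberal. That is a good reason for not making it the primary analysis.

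Four stronger readings are tempting and are not supported:

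- A reader might infer that participants are nested in a handful of fixed coaches. The documents give neither the number nor the assignment rule. If coaches rotate, the structure is multiple-membership, still correlated but not strictly nested.
- A reader might infer from the 90% fidelity trigger that the protocol expects coaches to differ in outcome. It is a safeguard on delivery and says nothing about outcomes.
- A reader might conclude that the interval for beta2 is too narrow. That holds only if the coach ICC is positive.
- A reader might take the low power figures in Section 7.7 as a hidden allowance for clustering. An intervention-arm design effect of 3 would halve the effective sample, since (3 + 1)/50 = 2/25, but no such allowance is stated.

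**Conclusion.** The point holds as a conditional one. More than one coach delivers the intervention, in one arm only, and the Aim 2 model makes no allowance for it. Any positive coach ICC makes the model-based standard error of beta2 too small for inference beyond the trial's own coaches.

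The documents cannot say by how much. The plausible range runs from nothing of consequence (10 or more coaches with a low ICC) to a true standard error 11% to 18% larger than planned (5 or 3 coaches, ICC 0.05) with full retention, or 8% to 13% larger at 75% retention. These figures rest on assumed coach numbers and ICCs, equal caseloads and one coach per participant.

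For a pilot whose main aim is estimation, and whose sample-size section already advises caution in interpreting the estimate, this is a cheap improvement. It does not invalidate the planned analysis.

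**What to change.** 1. State in the protocol how many coaches there are, how participants are assigned to them, and whether a participant normally keeps one coach.
2. Record coach ID for every intervention participant, and any change of coach.
3. Keep the planned repeated-measures model as the primary analysis.
4. Pre-specify a sensitivity analysis of beta2 with a random coach effect in the intervention arm only and small-sample degrees of freedom. Report its interval beside the primary one, with the estimated coach ICC and its confidence interval. If coach variance is estimated at zero, the point estimate reverts to that of the planned model.
5. Say in the report that, with few coaches, the ICC is imprecise and the corrected test may still be slightly liberal, and repeat this wherever the results are used to plan the next trial.

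The cost is one recorded variable and a short paragraph in Section 7.9. The statistical price is a wider second interval and, with few coaches, an ICC that may say little. No change to the sample size, the visits or the intervention is needed.

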5 STUDY ENROLLMENT AND WITHDRAWAL

The total target sample size for enrollment in Phase 1 is 125 participants and in Phase 2, 100 participants (50 participants per arm). A higher enrollment is expected for Phase 1 than Phase 2 to account for some participants being deemed ineligible to proceed with Phase 2.

Potential participants are identified through upcoming cardiology clinic rosters who meet the age (15-25 years of age) and diagnosis (moderate to complex CHD³) criteria. Study personnel check the patient's medical record to verify eligibility. If a patient appears to be eligible, study staff confirm with the attending cardiologist that no additional reason/s preclude the adolescent from participating, including limitations to engaging in MVPA. Next, the patient, or if an adolescent, the patient's caregiver(s) (or their legal guardian of record), is sent a letter from the attending cardiologist, notifying them about the study and that study personnel will be in contact. An "opt out" phone number is provided so that the caregiver(s) can call and leave a message if they do not wish to be contacted. Approximately 1 week later, if no message was received, caregiver(s) are called by study personnel. During the phone conversation, the objectives and primary components of the study are discussed. If a patient and/or caregiver are interested, verbal consent/assent (if <18 years of age) is obtained for completing online questionnaires and the exercise stress test at NCH is scheduled. During the stress test visit, written consent/assent for the stress test and accelerometer assessment is obtained. If a patient and/or a caregiver cannot be reached via phone, they are approached during their clinic appointment in person.

